- **Targeted screening:** During the targeted screening intervention, data from the SHS will be integrated into the EHR and will provide CDS for GC/CT testing based on SHS-calculated STI risk (developed and validated by [name]). Patients will be classified as at high risk for STIs if they disclose being sexually active and have either the presence of STI-related symptoms or any of the following high risk behaviors: more than 1 sexual partner in the last 3 months, no condom use during last sex or prior history of STI. Patients will be classified as at risk if they disclose being sexually active but do not disclose having any STI-related symptoms or any high-risk sexual behaviors. Patients will be classified as at low risk if they deny any history of sexual activity (see preliminary data for STI positivity rates by risk strata). When patients classify as at high risk, clinicians will receive CDS that STI testing is highly recommended; when they care for patients who classify as at risk, they will receive CDS that STI testing is recommended; when caring for patients who classify as at low risk, they will receive CDS that STI testing is not necessary at this time. If the clinician chooses to follow the recommendation for screening based on patients risk assessment, and the patient consents to testing on the tablet device, urine GC/CT testing will be performed.
- **Universally offered screening:** During the universally offered screening intervention, STI screening will be offered to all eligible adolescents, regardless of risk. All eligible patients will also complete the SHS, will be informed of the CDC GC/CT testing recommendations and then be given the option to decline STI testing using the tablet device. During this phase, the SHS results will not be available to the clinician. STI testing recommendations will be based only on the patients decision to undergo GC/CT testing. Like the process followed in the targeted screening phase, if the clinician follows the CDS that informs the clinician that the patient

agreed to GC/CT screening and consequently orders testing, urine GC/CT testing will be performed.

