4.2 Surveys

All data entered into the tablet by either the ED personnel or the patient will be stored at the study site. This information will include the patients medical record number, encounter ID, patients electronic consent to participate in the study, and survey responses. For those patients who either do not meet inclusion criteria or refuse participation, exclusion/refusal reasons will be documented by the staff and/or patients electronically and stored in this database.

During implementation of the targeted screening intervention, the patient responses to the SHS survey will categorize patients as at high risk, at risk, or at low risk for STIs. This composite score will then be transmitted to the EHR through the Bridges Interconnect system, a secure native interface allowing one-way transmission of data into Epic. Bridges Interconnect is used to send data outside the Epic EHR into the EHR and is available at all participating sites. CDS will be triggered on the EHR based on STI risk strata as calculated by the SHS. During implementation of the universally offered screening, CDS for GC/CT screening will be determined by the patients decision to be screened. If a patient agrees to GC/CT screening, that information will be transmitted to the EHR through the Bridges Interconnect system, which will then trigger GC/CT

screening CDS for the clinician.

5 Data Analysis

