5.1 Specific Aim Analyses

Specific Aim 1. To compare the effectiveness of usual care, targeted screening and universally-offered screening in EDs through a pragmatic trial that applies a human factors systems approach to implement GC/CT screening into routine clinical care.

Human Factors Workflow Analyses: Data will be aggregated across observations and workflow analysis will be performed to identify the most frequent tasks and interactions during an ED visit. Transition diagrams will be created to examine overall workflow processes which will include tasks performed, communication events between clinicians and patients, and interactions with technology. Common patterns of activity will be identified and used to inform deployment of the application to the patient and integration with the EHR.

Pragmatic Trial: We will report descriptive statistics to summarize each primary and secondary outcome variable. Our primary comparison of GC/CT screening strategies will be targeted vs. universally offered. We will compare detection rates (number of STIs detected divided by the number of eligible, asymptomatic patients) using site 2-week period as the unit of analysis. Standard stepped-wedge analysis techniques will be used. Specifically, the site detection rate over each 2-week period will be the outcome in a linear model to examine the effect of screening strategy on detection rate. In the model, we will include a fixed effect for each site. To control for temporal trends, we will model the effect of time as a piecewise linear function with 8 three-month segments (i.e., cutpoints at the following times on the two-week scale: 0.5, 7, 13.5, 20, 26.5, 33, 39.5, 46, and 52.5 weeks). A three-level intervention effect will be included, and we will test for a difference between targeted and universally offered screening at a 5% significance level. We will perform a similar analysis using the outcome of rate of positivity among those tested for GC/CT. We will also calculate the proportion of visits during which eligible patients agreed to GC/CT testing and compare them across the 2 STI screening strategies (targeted vs. universally offered). We will calculate the proportion of visits during which clinicians follow the GC/CT testing CDS recommendations across the 2 GC/CT screening strategies and will perform multivariable logistic regression to identify patient, clinician, and site-specific factors that may be associated with uptake of the CDS.

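### Clinician adherence to CDS is compared between strategies over different sets of visits, and no site- and time-adjusted strategy comparison is stated for adherence or for patient agreement

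*Combined protocol and SAP*

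**What the plan says.** In the targeted phase, section 4.2 states "CDS will be triggered on the EHR based on STI risk strata as calculated by the SHS". All three strata produce a message. For the lowest, section 4.1 says of clinicians that "when caring for patients who classify as at low risk, they will receive CDS that STI testing is not necessary at this time". Patient agreement is a further condition: a test follows if the clinician acts on the advice "and the patient consents to testing on the tablet device, urine GC/CT testing will be performed". Advice to test can therefore appear for a patient who has declined.

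In the universal phase, section 4.1 says "STI testing recommendations will be based only on the patients decision to undergo GC/CT testing", and section 4.2 says "CDS for GC/CT screening will be determined by the patients decision to be screened". The only transmission described is for agreement: "If a patient agrees to GC/CT screening, that information will be transmitted to the EHR through the Bridges Interconnect system", which then triggers the CDS. No message is described for a patient who declines.

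Section 5.1 then plans, for adherence: "We will calculate the proportion of visits during which clinicians follow the GC/CT testing CDS recommendations across the 2 GC/CT screening strategies". The same sentence adds a multivariable logistic regression of CDS uptake on patient, clinician and site-specific factors. For patient agreement the plan is to "calculate the proportion of visits during which eligible patients agreed to GC/CT testing and compare them across the 2 STI screening strategies", with no model named. Site fixed effects, piecewise-linear time terms and a strategy term are specified for the detection rate, and a similar analysis is extended to positivity among those tested, but not to agreement or adherence.

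**The concern.** The adherence proportion mixes different things in the two phases. The targeted phase can include visits where the advice is followed by doing nothing, and visits where testing was advised but the patient had already refused. The universal phase contains only patients who said yes, some of whom may never have been sexually active. A difference between the proportions may then reflect how the alert is triggered rather than how clinicians respond to it.

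Both comparisons are also exposed to site and calendar-time differences. In a stepped-wedge crossover, sites spend unequal time on each strategy, and within a site one strategy wholly precedes the other. At stake is a secondary conclusion about which strategy clinicians follow better, or patients accept more readily.

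**Working it through.** The plan gives no expected adherence, so there is no stated figure to reproduce. Only the share advised testing can be tied to the documents.

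**Inputs**
- r, share of targeted-phase visits where testing is advised: 1/3. Section 5.2 puts the targeted population at about 1/3 of asymptomatic patients; reading this as everyone advised testing is an assumption. The plan uses the share consistently: 1/3 × 10% = 3.3% and 1/3 × 14% = 4.7%, against its stated 3-5%.
- a, patient agreement: assumed 0.5 to 0.9. Section 2.2 says only that a majority accept testing.
- p, probability that the clinician orders when testing is advised and the patient agreed: assumed 0.6 to 0.9, identical in both phases.
- q, probability of no order when the message says testing is not needed: assumed 0.99.

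**Formulas.** Universal adherence is p. Targeted adherence depends on the scoring rule:
- A. All messages count, refusals scored as not followed: (1−r)q + r·a·p
- B. Only advice to test counts, refusals scored as not followed: a·p
- C. All messages count, refusals dropped: [(1−r)q + r·a·p] / [(1−r) + r·a]
- D. All messages count, clinician response scored whatever the patient chose: (1−r)q + r·p
- E. Only advice to test counts, clinician response scored whatever the patient chose: p

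**Targeted minus universal, in points**

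| Rule | At p = a = 0.70 | Range over the assumed p and a |
|---|---|---|
| A | 0.660 + 0.163 − 0.700 = +12.3 | −9 to +24 |
| B | 0.490 − 0.700 = −21.0 | −45 to −6 |
| C | 0.823/0.900 − 0.700 = +21.5 | +6 to +31 |
| D | 0.660 + 0.233 − 0.700 = +19.3 | +6 to +26 |
| E | 0.700 − 0.700 = 0 | 0 |

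The ends of range A are 0.66 + (1/3)(0.5)(0.9) − 0.90 = −0.09 and 0.66 + (1/3)(0.9)(0.6) − 0.60 = +0.24. For the others, B equals −p(1−a), D equals (1−r)(q−p), and C equals (q−p)(1−r)/[(1−r)+r·a].

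**Sensitivity to r.** The 1/3 describes asymptomatic patients, but the adherence endpoint is not limited to them. Section 5.2 expects 242 enrolled per block, 220 of them asymptomatic. If all 22 others were sexually active, r would be (220/3 + 22)/242 = 0.39, and range A becomes −12 to +21.

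**Rule E is not a full escape.** Its targeted denominator is sexually active patients, decliners included; its universal denominator is agreers, including the non-sexually active. If a fraction w of universal agreers is sexually active, and clinicians order for them at rate p₁ and for the rest at p₀, universal adherence is w·p₁ + (1−w)·p₀. Even with every targeted-phase response at p₁, the gap is (1−w)(p₁ − p₀), which is zero only if p₁ = p₀ or w = 1.

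**Site mix, for agreement.** One reconstruction of the example schedule in section 3.4 gives sites 1 to 6 17, 26, 24, 15, 22 and 11 targeted blocks (total 115) and 27, 16, 16, 23, 14 and 23 universal blocks (total 119). The root sum of squared differences between each site's share of targeted and of universal blocks is 0.198. A between-site SD in agreement of 5 to 10 points (assumed) then puts an SD of 1 to 2 points on a crude difference. With 242 patients per block and 70% agreement, the binomial standard error is √(0.21/27,830 + 0.21/28,798) = 0.4 points.

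**The case against.** Several counter-arguments have force.

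- Different triggers are part of the strategies, so how often clinicians act on each is a legitimate implementation outcome. This stands as a reason to keep the overall proportion as a description of each strategy, not to read its difference as a difference in clinician behaviour.
- Section 4.1 treats the clinician's choice and the patient's consent as separate conditions, and section 6.2 captures clinician actions and reasons for not following CDS. A refusal is then not naturally clinician non-adherence, and without that scoring the negative gaps lose their basis. This stands; the plan simply does not say.
- The endpoint could be read as advice to test only, with clinician response scored separately from refusal (rule E). The artefact then vanishes under identical behaviour, but the two patient groups still differ.
- The adherence sentence includes a regression with site-specific factors, so a reader who infers that adherence has no site adjustment at all goes too far. What is absent is strategy and time. The separate regression of testing consent names demographic and behavioural factors only. For agreement no method is given, so a crude comparison is an inference from silence.
- The schedule in section 3.4 is an example, the block counts are a reconstruction, and the between-site SD is assumed. In the example, three sites start with each strategy, which partly balances time.

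A reader might also infer a bias of 20 points in either direction as a property of the plan. The documents do not support that. With 1/3 advised testing, rule A does not go below −9 on the assumed grid. The −27 that rule A gives at r = 2/3 (0.33 + 0.30 − 0.90) reverses the plan's own share. Both signs at about 20 points appear only by changing the scoring rule.

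**Conclusion.** The point holds in a limited form. As described, the two adherence proportions rest on different visit populations, so identical clinician behaviour can produce different results. Sign and size depend on undefined scoring rules and on rates the documents do not give: about −9 to +24 points under rule A with r = 1/3, and about +20 or −20 under other rules when ordering and agreement are both 0.70. These are illustrations, not predictions, and the gap can be small or zero. That CDS is silent for universal-phase decliners is inferred from section 4.2, not stated outright.

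The adjustment gap also holds: no site or time adjustment is stated for comparing agreement, and the CDS-uptake regression names neither strategy nor time. Its size cannot be established from the documents. Both comparisons are secondary, with no stated test or power, and the primary detection analysis is untouched. The change should be made, but the trial's main conclusion does not depend on it.

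**What to change.** 1. For the between-strategy comparison, define adherence in both phases as testing ordered among visits where the patient reported sexual activity on the SHS and agreed to testing on the tablet. With this denominator r, a and q drop out of the comparison. That the gap becomes zero is simply the assumption of equal p; the gain is that only clinician response on comparable visits remains.
2. Report separately the responses to messages that testing is not needed, patient refusals, and universal-phase CDS for agreers who are not sexually active. Keep each strategy's overall proportion as descriptive.
3. Compare agreement and adherence with the primary outcome's site fixed effects and piecewise-linear time terms. The strategy term has two levels here, because the tablet process is described only for the two screening phases.

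The cost is SAP wording. The SHS and tablet choice are collected in both phases (sections 4 and 4.1), and orders and CDS actions are merged with them by encounter (section 6.2). The drawback is that adherence is then conditional on agreement, which the strategy may itself affect, so the agreement comparison must be shown beside it.

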As additional secondary outcomes, for patients who consent to SHS completion, we will perform multivariable logistic regression to identify demographic and behavioral factors associated with GC/CT testing consent and GC/CT positivity.

Specific Aim 2. To determine the most cost-effective approach for GC/CT detection (i.e. usual care, targeted screening, and universally-offered screening) in an adolescent ED population.

Cost-effectiveness analysis: Markov state transition models will be built using readily available software (Decision Maker, Boston, MA). Health states will include those that impact prognosis, cost and quality of life, such as asymptomatic and symptomatic infection with GC and/or CT, pelvic inflammatory disease, infertility, ectopic pregnancy, and chronic pelvic pain. Because the median ED LOS for an adolescent is 4.25 hours, and we have previously demonstrated no significant difference in LOS between patients who completed the SHS compared to those who did not,¹⁷ time to complete survey will not be entered into the model. Furthermore, during a 4-hour ED visit, there is ample time to collect a urine sample, and urine testing is often already requested for clinical care. Therefore, time to obtain samples will also not be included in the cost analysis. We will use a one-month cycle length and a life-long time horizon. Patients will move between health states over time depending upon events that occur in each one-month cycle of the simulation. Health states and events will have associated quality of life and costs. We will perform analyses first using base case estimates for all parameters. We will next perform deterministic sensitivity analyses, examining key parameters one, two, or three at a time, to explore the impact of uncertainty and to address other plausible scenarios, such as populations with lower or higher prevalence of STIs. We also will be able to test various cut points for the STI risk prediction tool, described in aim 2, to see if there is an optimal cut point that minimizes the incremental cost-effectiveness ratio, finding the best balance between sensitivity and specificity for the risk prediction tool. Finally, we will perform probabilistic sensitivity analyses, using second order Monte Carlo modeling, to generate cost-effectiveness acceptability curves, providing further insights into the proportion of the time that the winning strategy will be cost-effective.

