5.2 Sample Size Calculations and Statistical Power

Workflow Analyses: We estimate that we will observe between 20-30 individuals per site, which is a common sample size for studies of ED workflow processes.

Difference	Power
0.5%	80%
0.75%	98%
1%	99%

Table 2: Power Calculations

Pragmatic Trial: We plan to enroll at 6 PECARN sites. Based on PECARN data, with 6 sites for 52 two-week periods, we conservatively anticipate that approximately 288 patients or more per two weeks per site will arrive. Of these, we conservatively expect to enroll 242 per site. About 220 of these will be asymptomatic and included in the primary analysis. Our preliminary data reveal STI screening rates of 0.16% (usual care) leading to detection rates less than 0.02%. Asymptomatic STI detection rates range from 4-10% in a population of universally offered screening. In a targeted population, which makes up about 1/3 of the overall asymptomatic population, 10-14% will test positive. This leads to estimated detection rates of approximately 3-5%. For power calculations, we assume a detection rate of 4.5% using a targeted strategy and a standard deviation in rates across sites of 2%. Based on expected enrollment of 220 asymptomatic patients per time period per site, we will have approximately 99% power to detect a 1% difference in detection rates, and over 80% power to detect a difference as small as 0.5% between targeted and universally offered strategies (see table above). A 1% difference in detection corresponds to approximately 450 additional STIs detected per year at these sites alone. If results from this study inform screening at centers across the country, the numbers captured could be orders of magnitude higher. Additionally, we will also have adequate power for subgroup analyses based on gender, age, race/ethnicity, and symptomatology, as the design will provide over 90% power to show a difference in detection rates of 2% for subgroups as small as 40 patients per month. Confidence intervals around detection rates in each of the screening strategy groups will be smaller than +/- 0.3%.

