6.2 Electronic Data Capture System

The Data Coordinating Center (DCC) will develop an electronic data capture system for this trial. Currently the DCC uses multiple applications, such as OpenClinica or REDCap, and will elect to use the most appropriate application at the time of implementation of the study. Data will be entered by each clinical site.

The DCC will use an electronic discrepancy management system to notify sites of inconsistent or erroneous data entry, which will be corrected by the clinical site. The discrepancy management system maintains an audit trail of all discrepancy resolution.

All study information requiring EHR abstraction will be accessed through Epics Clarity, a SQL-based querying tool available to all Epic sites. Data will include the patients medical record number, encounter ID, demographics, STI orders, GC/CT results, and information associated with the firing of the CDS (i.e. user, actions taken, time fired, refusal reasons for the clinician not following the CDS), and follow up treatment data. In addition to GC/CT test results, we will also abstract test results from any other STI test that may have been ordered by the clinician, including testing for Trichomoniasis, Herpes Simplex Virus, Syphilis, and HIV. These data will be merged with the tablet data using the patient encounter ID for all adolescents who agree to participate.

Data will be abstracted daily during study implementation for quality checks and then weekly via a CSV file. The data manager at each site will compile the data through this automated process and results will be stored securely, accessible only by study staff. The data from the application database and EHR database will be automatically merged by matching the patient encounter IDs as a unique identifier. SQL code for this automated merge was developed by [name] at CCHMC and will be shared with each site. The merged data at each site will then be stripped of patient names and a unique study ID number will be attached to each encounter. This unique study ID will allow linkage of the databases to allow for confirmation of data in the event of data queries from the DCC. The study team will develop a Manual of Operations for participating sites which will include creation of data dictionaries, data transfer instructions, methods of encryption

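### The logistic model for uptake of the decision support states no method for clustering by clinician and site, so as written it understates the uncertainty of clinician-level and site-level factors

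*Combined protocol and SAP*

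**What the plan says.** Section 5.1 (Pragmatic Trial) defines the outcome at the visit: "We will calculate the proportion of visits during which clinicians follow the GC/CT testing CDS recommendations". For its predictors, the plan says the team "will perform multivariable logistic regression to identify patient, clinician, and site-specific factors that may be associated with uptake of the CDS". That clause is the whole specification. Neither section 5.1 nor any other section names a random effect, generalized estimating equations, a clustered or robust variance, or an ICC for this model.

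The same section does deal with site in the primary analysis, a linear model of two-week site detection rates: "In the model, we will include a fixed effect for each site". The only significance level is also attached to that analysis: "we will test for a difference between targeted and universally offered screening at a 5% significance level". Neither statement is carried over to the CDS-uptake model.

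Section 5.2 gives the number of sites: "We plan to enroll at 6 PECARN sites". Section 6.2 lists among the items abstracted from the health record "information associated with the firing of the CDS (i.e. user, actions taken, time fired", so the clinician responding to each alert should be identifiable.

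**The concern.** Whether an alert is followed is a clinician's decision, and each clinician makes it at many visits. Clinicians differ in how readily they follow alerts, so visits handled by the same clinician are likely to be correlated. A clinician characteristic does not change over those visits. The information about its effect therefore comes mainly from the number of clinicians, while a logistic model with its default standard errors counts visits. The same holds more strongly for a site-level covariate, where there are six independent units and thousands of visits.

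Clinician and site factors are two of the three kinds of predictor that the plan sets out to identify, and they are the kinds whose standard errors suffer most. At stake is whether the study's account of which clinicians and sites take up the decision support separates real associations from differences between individual clinicians or sites.

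**Working it through.** The documents give no sample size, power, ICC or error rate for this model, so there is no stated figure to reproduce. The check asks how often a nominal two-sided 5% test would reject when there is no association. The 5% level is itself an assumption here.

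**Visits per site.** Section 5.2 gives "6 sites for 52 two-week periods", that is 6 × 52 = 312 site-periods, and expects 242 enrolled per site per period. Reading the example schedule in Figure 2 (section 3.4) as 54 baseline, 12 ramp-up and 12 washout site-periods leaves 312 − 54 − 12 − 12 = 234 active site-periods. Then 234 × 242 = 56,628 enrolled visits, or 56,628 / 6 = 9,438 per site. Not every enrolled visit produces an alert: in the universally offered phase the alert is triggered when the patient agrees to testing (section 4.2). I therefore take one third of enrolled visits (3,146 per site) as a lower bound and all of them as an upper bound.

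**Assumed, not in the documents.** 30 to 150 clinicians per site; clinician ICC 0.01 to 0.10; site ICC 0.001 to 0.05.

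**Formulas.** With m visits per cluster and a covariate constant within the cluster, the design effect is DE = 1 + (m − 1) × ICC. The unadjusted test then rejects with probability 2 × [1 − Φ(1.96/√DE)] under the null.

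**Clinician-level factor** (DE, then rejection rate):

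| Visits analysed | Clinicians per site | m | ICC 0.01 | ICC 0.05 | ICC 0.10 |
|---|---|---|---|---|---|
| One third | 150 | 21 | 1.2, 7% | 2.0, 17% | 3.0, 26% |
| One third | 60 | 52 | 1.5, 11% | 3.6, 30% | 6.1, 43% |
| One third | 30 | 105 | 2.0, 17% | 6.2, 43% | 11.4, 56% |
| All | 150 | 63 | 1.6, 12% | 4.1, 33% | 7.2, 47% |
| All | 60 | 157 | 2.6, 22% | 8.8, 51% | 16.6, 63% |
| All | 30 | 315 | 4.1, 34% | 16.7, 63% | 32.4, 73% |

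**Site-level covariate:**

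| m per site | ICC 0.001 | ICC 0.01 | ICC 0.05 |
|---|---|---|---|
| 3,146 | 4.1, 34% | 32.5, 73% | 158, 88% |
| 9,438 | 10.4, 54% | 95.4, 84% | 473, 93% |

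**Simulation check.** Null data were simulated with six sites, 60 or 150 clinicians per site, mean volumes of 20 to 150 visits per clinician (unequal between clinicians), 60% uptake and 1,000 runs per setting. ICCs were set on the latent logistic scale, so they do not match the formula's one for one. With clinician ICC 0.01 to 0.10 and site ICC 0.005 to 0.05:

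- Unadjusted model, clinician-level factor: 8% to 72%.
- Unadjusted model, site-level covariate: 60% to 93%.
- Site fixed effects with unadjusted standard errors, clinician-level factor: 7% to 68%.
- Site fixed effects with standard errors clustered on clinician: 3.7% to 7.6%.

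With both ICCs at zero, the rejection rates stayed near 5%. The random-intercept version was not simulated.

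**The case against.** The strongest reply is that the plan never says visits will be treated as independent. Multivariable logistic regression names a family of models, and a random-intercept or estimating-equation version would fit the wording. The clause is short, the analysis is exploratory, no significance level is set for it, and none of the hypotheses in section 1.1 concerns uptake of the decision support. All of this is correct. A reader might infer that the plan prescribes an independence model or rules out use of the clinician identifier; the text supports neither. What remains is that the method as named, fitted without anything further, is wrong for two of the three kinds of factor it lists, and nothing in the documents directs the analyst otherwise.

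Other stronger readings also fail:

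- **All site results would be invalid.** If site-specific factors means indicators for the six sites, contrasts among those sites are estimable and the site clustering is absorbed. Clinician-level inference is still anti-conservative (7% to 68% in the simulation).
- **The inflation is always large.** At a clinician ICC of 0.01 and about 20 visits per clinician it is 7% to 8%, close to nominal.
- **Each site contributes over 9,000 alert visits.** That figure counts enrolled visits under a schedule that section 3.4 presents as an example.
- **The consent and positivity models share the fault.** Section 5.1 says "we will perform multivariable logistic regression to identify demographic and behavioral factors associated with GC/CT testing consent and GC/CT positivity". Those predictors are patient characteristics that vary within clinician and site, so the argument about cluster-constant covariates does not carry over.
- **The regression would steer practice elsewhere.** Section 2.2 links use in other departments to the workflow analyses, not to this model.

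**Conclusion.** The point stands as a gap in the specification with a predictable direction of error. As written, the CDS-uptake model would give standard errors that are too small for clinician-level factors and for any site-level covariate. The size cannot be fixed from the documents. Over the assumed ranges, the null rejection rate of a nominal 5% test runs from near nominal to very high for clinician-level factors. For a site-level covariate it is severe throughout. The visit totals are approximate because they depend on the example schedule and on how many visits produce an alert; the direction does not depend on them. The analysis is secondary, and the primary test of targeted against universally offered screening does not rest on it.

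**What to change.** In section 5.1, specify that the CDS-uptake model will include site fixed effects and either a random intercept for clinician or standard errors clustered on clinician, with clinician defined by the alert user already abstracted under section 6.2. Either form deals with the clinician clustering; of the two, only the clustered-variance form was checked by simulation.

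State also that site-level covariates will be described without p-values. They are collinear with site fixed effects, and even without those effects six sites leave about 4 degrees of freedom (6 − 2) for one covariate.

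This is a change of wording and needs no new data. The cost is wider intervals for clinician factors, which reflect the information actually available, and the loss of any formal test of site-level covariates.
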